However, there is a subgroup of subjects who have an identifiable cause for hyponatremia that has not (or cannot be) changed that will have an option to be excused from this brief interruption of tolvaptan. Examples of such causes include concomitant treatment for refractory seizures with a hyponatremia-inducing medication such as oxcarbazepine (which can increase vasopressin production by the pituitary) that cannot be changed or discontinued, or subjects with a known underlying hyponatremia inducing condition such as volume overload from a failing Fontan repair.

During this treatment interruption, subjects will have serum sodium levels monitored closely. Subjects who demonstrate a decline in serum sodium level will be restarted at the prior dose of tolvaptan as per clinician judgment. Subjects whose serum sodium declines ≥ 4 mEq/L (mmol/L) or who exhibit symptoms of hyponatremia will be immediately placed under direct observation as per clinician judgment and will be restarted at their previous dose of tolvaptan unless there is a compelling reason to reduce the dose. Subjects will be closely monitored until stable.

Investigators should consider the overall clinical status of the subject (including underlying etiology of hyponatremia and volume assessment), prior response to tolvaptan, concomitant medications, age, and weight when determining the appropriate dose at which to restart a subject after a brief discontinuation of tolvaptan to assess the need for further treatment. Investigators should discuss any concerns with the medical monitor.

- Subjects who resume dosing within 72 hours post last dose (either on Day 32 or by the morning of Day 33), can do so at the same dose or a lower dose without having to go through the full titration cycle again.
- Subjects who have a dosing interruption of ≥ 72 hours must enter a new treatment cycle and repeat the full titration cycle in a hospital setting.
- Subjects who do not need to continue treatment with tolvaptan will proceed directly to the Follow-up Phase (Day 7 Follow-up). Subjects will then continue in the core safety follow-up component and complete remaining required visits, as applicable.

The optional tolvaptan treatment component of the trial will be available for the 6-month duration of the core safety component for each subject.

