3.2.1.2 Titration Guidelines for the Optional Tolvaptan Treatment Component

In the optional tolvaptan treatment component of the trial, eligible subjects will receive tolvaptan based on age, weight, and the use of CYP3A4 inhibitors. Tolvaptan tablets will be administered orally QD, preferably in the morning hours.

Tolvaptan doses can be titrated QD and will be based on serum sodium levels assessed at 24 (\pm 4) hours following initiation of therapy and each subsequent dose. Titration guidelines are detailed in [Figure 3.2.1.2-1](#). Titration must occur in a hospital setting. Titration may not occur within 24 (\pm 4) hours of the previous dose and must be based on serum sodium assessment obtained $>$ 20 hours post previous dose. Titration is limited to no more than twice the previous dose, and will be limited to the maximum dose per body weight.

An age-appropriate formulation is not available for this trial. Therefore, the following subjects will be excluded from the optional treatment component of this protocol:

- Subjects $<$ 4 years of age, or weighing $<$ 10 kg,
- Subjects with an inability to swallow tablets, and
- Subjects weighing $<$ 20 kg and taking a moderate or potent CYP3A4 inhibitor

[Table 3.2.1.2-1](#) outlines starting tolvaptan doses and adjustments when tolvaptan is administered concurrently with potent or moderate CYP3A inhibitors. Tolvaptan doses will be reduced 75% and 50% if a potent or moderate inhibitor, respectively, is being concurrently administered.

Table 3.2.1.2-1 Starting Tolvaptan Doses With or Without Potent or Moderate CYP3A4 Inhibitors				
Age/Weight	Can subject swallow a tablet?	Starting Dose: No CYP Inhibitor	Starting Dose: Moderate CYP Inhibitor	Starting Dose: Potent CYP Inhibitor
≥ 4 y AND ≥ 10 to < 20 kg	Yes	3.75 mg	Not eligible for treatment	Not eligible for treatment
≥ 4 y AND ≥ 20 to ≤ 50 kg	Yes	7.5 mg	3.75 mg	Not eligible for treatment
≥ 4 y AND > 50 kg	Yes	15 mg	7.5 mg	3.75 mg

Based on the weight versus dose information provided in [Table 2.2-1](#) and taking into consideration the concomitant use of a CYP3A4 inhibitor, the starting doses are as follows:

Subjects ≥ 4 years of age and weighing ≥ 10 to < 20 kg:

- Not taking a moderate or potent CYP3A4 inhibitor will receive a QD oral tolvaptan tablet dose of 3.75 mg, with possible up-titration to 7.5 mg and 15 mg
- Taking a moderate or potent CYP3A4 inhibitor are not eligible for optional tolvaptan treatment

Subjects weighing ≥ 20 to ≤ 50 kg:

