- Not taking a moderate or potent CYP3A4 inhibitor will receive a QD oral tolvaptan tablet dose of 7.5 mg, with possible up-titration to 15 mg and 30 mg
- Taking a moderate CYP3A4 inhibitor will receive half the starting tolvaptan tablet dose, eg, 3.75 mg tablet, with possible up-titration to 7.5 mg and 15 mg.
- Subjects are not eligible to receive optional tolvaptan treatment if they are taking a potent CYP3A4 inhibitor.

Subjects weighing > 50 kg

- Not taking a moderate or potent CYP3A4 inhibitor will receive a QD oral tolvaptan tablet dose of 15 mg, with possible up-titration to 30 mg and 60 mg
- Taking a moderate CYP3A4 inhibitor will receive half the starting tolvaptan tablet dose, ie, 7.5 mg, with possible up-titration to 15 mg and 30 mg

- Taking a potent CYP3A4 inhibitor will receive one quarter the starting tolvaptan tablet dose, eg, 3.75 mg, with possible up-titration to 7.5 mg and 15 mg.

Subjects not eligible for the optional tolvaptan treatment component still remain eligible for the core safety follow-up component.

Subjects eligible for the optional tolvaptan treatment component will titrate according to the guidelines listed in [Figure 3.2.1.2-1](#), targeting a final serum sodium concentration between 135 and 140 mEq/L (mmol/L). The clinician-directed target range is also acceptable.

Treatment can be discontinued at any time and cycles may be repeated as needed. If subjects are off tolvaptan treatment for ≥ 72 hours, re-initiation of tolvaptan treatment, starting with the pre-treatment baseline visit will occur. This will require a reassessment of the eligibility criteria, a tolvaptan titration period, and will begin in a hospital setting as part of a new treatment cycle.

The titration scheme is shown in [Figure 3.2.1.2-1](#).

[figure not shown]

Figure 3.2.1.2-1 Titration Scheme

Titration guidelines are designed to ideally achieve a change in serum sodium concentration of at least 4 to 8 mEq/L (mmol/L) /24 hours but not \geq 12 mEq/L (mmol/L)/24 hours.

Tolvaptan dose titration (after the initial dose) must be based on changes in serum sodium levels as follows:

- If the serum sodium level increases by \leq 4 mEq/L (mmol/L)/24 hours and the subject is still below the therapeutic target for serum sodium level (135 mEq/L [mmol/L]), then the tolvaptan dose may be titrated up to the next scheduled dose.

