3.2.2 Rescue Therapy

Rescue therapy is defined as any treatment, eg, hypertonic saline, isotonic saline (with or without diuretic for the purpose of increasing the serum sodium level), plasmapheresis/dialysis, demeclocycline, urea, lithium, or commercial vaptans intended to raise the level of serum sodium during the trial. Subjects who develop worsening hyponatremia symptoms may receive rescue therapy at any time during the trial. However, subjects who require rescue therapy during the optional treatment component will be discontinued from tolvaptan prior to receiving rescue therapy.

Subjects will continue to be followed per the schedule of assessments in the optional tolvaptan treatment component (Follow-up Phase visits). Treatment with tolvaptan may be reinitiated only per consultation with the medical monitor. Subjects who have received rescue therapy because of inadequate response to tolvaptan will not be allowed to reinitiate tolvaptan treatment.

For subjects participating in the optional tolvaptan component only, serum sodium values drawn up to, but not after, the initiation of rescue therapy will be included in the

calculation of the efficacy endpoint. Additional guidelines for rescue therapy concerning hyponatremia symptoms and decreasing serum sodium level are as follows:

- If a subject has worsening symptoms and/or has a serum sodium level at or below the baseline value for the current treatment cycle, repeat serum sodium immediately (STAT) to confirm level, and begin rescue therapy.
- If a subject is asymptomatic and serum sodium has decreased by ≥ 4 mEq/L (mmol/L), but is still above the baseline value, consider need for rescue therapy according to local standard of care.
- If a subject is asymptomatic and serum sodium has decreased by ≤ 3 mEq/L (mmol/L) but is still above the baseline value, no action is required.

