Symptoms include headache, nausea and vomiting, weakness, confusion, altered consciousness, and lethargy and may progress to more advanced symptoms, including seizures, coma, and death, if untreated. Subjects with overt symptoms of hyponatremia that require immediate intervention to raise serum sodium acutely will be ineligible for tolvaptan treatment; this syndrome is rapidly reversible with hypertonic saline administration.

Additionally, those subjects who are at risk of developing cerebral demyelination will be ineligible for tolvaptan treatment, including subjects who have severe hyponatremia

≤ 120 mEq/L (mmol/L), hypernatremia, hypoxemia, severe liver disease, alcoholism, severe burns, severe malnutrition, hypokalemia, diabetes, or renal failure.^{4,21}

Subjects eligible for treatment with tolvaptan will be identified based on serum sodium concentrations that persist at levels < 130 mEq/L (mmol/L). Upon determination of eligibility, each subject's serum sodium will be reassessed just before tolvaptan administration to confirm it remains below this threshold prior to intended treatment initiation.

If any serum sodium value obtained during the pretreatment baseline period for tolvaptan treatment is ≥ 130 mEq/L (mmol/L), the subject will be ineligible for tolvaptan administration at that time.

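### Sections 3.1.2.1 and 3.2.1.2 can restart or raise tolvaptan in a child whom Section 3.2.2 sends to rescue therapy, and no readable text says which rule comes first

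*Protocol*

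**What the plan says.** Section 3.2.2 lists three guidelines under the lead-in "Additional guidelines for rescue therapy concerning hyponatremia symptoms and decreasing serum sodium level are as follows". The first applies to worsening symptoms and/or a sodium "at or below the baseline value for the current treatment cycle, repeat serum sodium immediately (STAT) to confirm level, and begin rescue therapy". The second and third concern asymptomatic children whose sodium has fallen but is still above baseline. A child who needs rescue in the optional component is taken off tolvaptan first, and reinitiation requires consultation with the medical monitor. In addition, "Subjects who have received rescue therapy because of inadequate response to tolvaptan will not be allowed to reinitiate tolvaptan treatment".

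Section 3.1.2.1 covers the planned interruption after 30 days. A child whose sodium declines is restarted at the prior dose at the clinician's judgment. If the decline is 4 mEq/L or more, or there are symptoms of hyponatremia, the child is placed under direct observation and "will be restarted at their previous dose of tolvaptan unless there is a compelling reason to reduce the dose".

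Section 3.2.1.2 governs titration. A dose change cannot come earlier than the dosing interval allows "and must be based on serum sodium assessment obtained" more than 20 hours after the previous dose. If sodium has increased by 4 mEq/L or less in 24 hours and is below 135 mEq/L, "then the tolvaptan dose may be titrated up to the next scheduled dose".

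The baseline for a cycle is the STAT value taken 2 to 4 hours before the first dose, which must be below 130 mEq/L (Section 3.7.3.2 and Appendix 5).

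**The concern.** The same confirmed sodium can satisfy the rescue rule and a rule that restarts or raises tolvaptan. Two sites, each following a section of the protocol, could then act differently on the same child: one restarts or up-titrates, the other withholds tolvaptan, gives rescue and may bar the child from further treatment. That is a safety matter to settle before these rules are used again in children.

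There is also a statistical consequence during titration. The percentage of subjects requiring rescue while on tolvaptan is a prespecified secondary endpoint (Protocol 3.5.2.1 and 7.4.2; SAP 5.1.7.1). If sites read the two sections differently, that percentage partly measures the reading.

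**Working it through.** The plan states no figure on this point, so the check sets the conditions side by side. The sodium values below are illustrations in whole mEq/L, not trial data.

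**Does the rescue rule reach an asymptomatic child?** Yes. The first guideline joins symptoms and level by and/or, so the level alone is enough once confirmed. The other two are limited to levels above baseline.

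**Is a child at or below baseline always under the titration target?** Yes. Baseline is below 130, so the highest whole value is 129, and 135 − 129 = 6. The condition of being below 135 is always met.

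**Conditions.** Let b be the cycle baseline, p the earlier value and c the current value.

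- Rescue, asymptomatic: c ≤ b, confirmed.
- Day 30 restart, asymptomatic: p − c ≥ 4.
- Up-titration: c − p ≤ 4 over 24 hours and c < 135. A strict reading of an increase also needs c − p > 0.

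| Setting | b | p | c | Restart or up-titration condition | Rescue condition |
|---|---|---|---|---|---|
| Day 30 interruption | 128 | 133 | 128 | met: 133 − 128 = 5 | met: 128 ≤ 128 |
| Day 30 interruption | 128 | 133 | 129 | met: 133 − 129 = 4 | not met: 129 > 128, so the second guideline applies (consider rescue) |
| Day 2 trough, no change counts as 4 or less | 127 | 127 | 127 | met: 0 ≤ 4, 127 < 135 | met: 127 ≤ 127 |
| Day 2 trough, true rise required | 127 | 127 | 127 | not met: rise is 0 | met |
| Day 3 trough, true rise required | 127 | 125 | 127 | met: rise is 2 | met: 127 ≤ 127 |

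**Day 30.** The interruption belongs to the treatment cycle (Section 2.1.2), so the cycle baseline still applies. The two rules meet when the decline ends at or below baseline. They also meet on symptoms alone, since worsening symptoms are symptoms. Scheduled draws fall at 24, 48 and 72 hours after the Day 30 dose (Days 31 to 33).

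**Titration.** Troughs are drawn on Days 2, 3 and 4.

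- If no change counts as an increase of 4 or less, an unchanged trough at or below baseline meets both rules. Day 2 is the cleanest case. A value unchanged over 24 hours on Day 3 or 4 means that the previous trough was already at or below baseline.
- If a true rise is required, Day 2 cannot collide: p = b, so c > b. On Day 3 or 4, c ≤ b and c > p give p < b. The previous trough was itself below baseline and was either not confirmed or not acted on.

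**Does other text set an order?** The Day 2 to Day 4 steps under Section 3.7.3.2.2 require the trough to be reviewed before dosing and refer to the titration guidelines only. The Day 31 to 33 steps (3.7.3.2.4.1 to 3.7.3.2.4.3) cite Section 3.2.1 for the continuation decision, not 3.1.2.1 or 3.2.2. Sections 3.7.5.8 and 3.8.3 mention rescue without ranking it. Sections 3.1.2.1 and 3.2.2 do not cite each other.

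**The case against.** A reader might infer that the titration and rescue sections give opposed orders. They do not. Section 3.2.1.2 only permits a higher dose, so a site that starts rescue breaches nothing in it. Section 3.7.5.8 makes the need for rescue a focus of clinical assessment, and Section 3.8.3 requires prompt notice to the medical monitor. This reduces the titration limb to an unordered overlap. It does not remove it, because a permission does not say that the other rule takes precedence.

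On Day 30, Section 3.1.2.1 is the more specific text, leaves part of the decision to the clinician and sends concerns to the medical monitor. Falling sodium is also what the interruption is meant to reveal, and the child is already off drug, so discontinuing before rescue fits awkwardly. These points favour reading 3.1.2.1 as self-contained, but no text says so, and the rescue guideline has no exception for the interruption.

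Figure 3.2.1.2-1, to which Section 3.2.1.2 sends the site for titration, is not shown, nor is Figure 3.1-1. Either might set an order. This objection stands and limits confidence.

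A reader might also infer a bias in the primary endpoint, because "serum sodium values drawn up to, but not after, the initiation of rescue therapy will be included in the" calculation of the efficacy endpoint. The documents do not support a size: SAP 5.1.6.1 names no particular summary, and SAP 5.1 says that the efficacy analyses will not be applied to this component.

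**Conclusion.** The point holds as a minor protocol inconsistency, with moderate confidence. It is sharper in the Day 30 interruption, where both sections direct an action. During titration it is a permission meeting a directive, and whether it arises at the first trough depends on whether no change counts as an increase of 4 mEq/L or less.

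It would be tempting to attach a share of affected children. The documents give no distribution of sodium or response in children from which one could be derived, so none is claimed. Nor does the effect on the rescue percentage clearly extend to Day 30: that endpoint counts rescue while on tolvaptan, and the child is then off it.

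SAP 5.1 states that no subject received optional tolvaptan, so no reported result is affected. The conclusion rests on the readable text alone.

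**What to change.** The sponsor should reconcile Sections 3.1.2.1, 3.2.1.2 and 3.2.2 so that a confirmed sodium at or below the cycle baseline, or worsening symptoms, leads to one stated action in titration and one in the Day 30 interruption. Its clinicians choose the actions; this review takes no position on them. The three sections should cite each other, and the Day 2 to 4 and Day 31 to 33 steps should cite whichever rule governs. If the two figures already set an order, the text should repeat it.

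The cost is one protocol clarification. No reported result changes.

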3.2.3 Fluid Restriction

Fluid restriction can be a standard of care in both the core safety follow-up component and the optional tolvaptan treatment component of the trial.

The option of initiating fluid restriction (all fluids) to ≤ 1 liter/day for tolvaptan-treated subjects with serum sodium < 130 mEq/L (mmol/L) is available at the investigator's discretion. Fluid restriction (limit per day) will be recorded (if available and applicable) on the electronic case report form (eCRF).

Fluid restriction must not be initiated for at least the first 24 hours after tolvaptan administration in order to determine the rate and magnitude of serum sodium change. A supplemental serum sodium assessment is scheduled 8 (-1 to $+ 0.25$) hours following the first dose of tolvaptan to provide additional information which may be used to guide the decision to initiate fluid restriction in the future.

3.3 Trial Population

3.3.1 Core Safety Follow-up Component

Approximately 100 male or female subjects will be enrolled in this trial. All subjects must have participated in a previous tolvaptan pediatric hyponatremia trial.

All subjects will be observed for safety for 6 months regardless of treatment status. Subjects enrolled in the core safety component may be eligible to receive optional tolvaptan treatment during the 6-month core safety component (see [Appendix 5](#) for optional tolvaptan treatment component eligibility requirements).

3.3.2 Optional Tolvaptan Treatment Component

Subjects enrolled in the core safety follow-up component of the trial may be eligible for treatment with tolvaptan. These subjects include, but are not limited to, those diagnosed

and admitted to a hospital for treatment of heart failure, hepatocellular disease (including cirrhosis), or SIADH/other. Subjects with acute hyponatremia or hyponatremia expected to resolve spontaneously will be ineligible for tolvaptan treatment. Children with an impaired ability to sense or communicate their thirst will either be required to undergo closer observation, laboratory and urine output monitoring, or will be ineligible for tolvaptan treatment if this is not possible. Children with hypovolemic hyponatremia or those who are at risk of such, secondary to any underlying conditions that cause volume depletion, are ineligible for tolvaptan treatment.

Hyponatremia Etiology in Children and Adolescents

Children with Factor V Leiden or Factor VII abnormalities may be eligible for treatment only if the benefit is judged to outweigh any risk. Tolvaptan may be administered to children with hepatocellular disease (including cirrhosis) who have platelet counts between 50,000 and 100,000/ μ L if the need to treat is felt to outweigh the increased risk of GI bleeding.

Children can develop symptomatic hyponatremia more frequently than adults and at less severe levels of hyponatremia because of the large brain volumes in relatively small skulls. The most serious consequence of hyponatremia is hyponatremic encephalopathy, which occurs in over 50% of children with serum sodium < 125 mmol/L.²¹

Hyponatremic encephalopathy is seen in hospitalized children and adolescents in association with SIADH or in the postoperative period. Hyponatremic encephalopathy is a medical emergency that requires immediate intervention;^{4,22,23} thus, subjects with known risk factors for developing hyponatremic encephalopathy may be ineligible for tolvaptan treatment (eg, hypoxia, infection, brain injury, neurosurgery, uncontrolled seizure disorders, cerebritis, encephalopathy, central nervous system disorders such as cytotoxic and vasogenic cerebral edema, unstable space-occupying brain lesion, or elevated AVP levels).

Symptoms include headache, nausea and vomiting, weakness, confusion, altered consciousness, and lethargy and may progress to more advanced symptoms, including seizures, coma, and death, if untreated. Subjects with overt symptoms of hyponatremia that require immediate intervention to raise serum sodium acutely will be ineligible for tolvaptan treatment; this syndrome is rapidly reversible with hypertonic saline administration.

Additionally, those subjects who are at risk of developing cerebral demyelination will be ineligible for tolvaptan treatment, including subjects who have severe hyponatremia

≤ 120 mEq/L (mmol/L), hypernatremia, hypoxemia, severe liver disease, alcoholism, severe burns, severe malnutrition, hypokalemia, diabetes, or renal failure.^{4,21}

Subjects eligible for treatment with tolvaptan will be identified based on serum sodium concentrations that persist at levels < 130 mEq/L (mmol/L). Upon determination of eligibility, each subject's serum sodium will be reassessed just before tolvaptan administration to confirm it remains below this threshold prior to intended treatment initiation.

If any serum sodium value obtained during the pretreatment baseline period for tolvaptan treatment is ≥ 130 mEq/L (mmol/L), the subject will be ineligible for tolvaptan administration at that time.

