3.1.2 Optional Tolvaptan Treatment Component

Subjects enrolled in the 6-month core safety follow-up component may be eligible to receive optional tolvaptan treatment for their hyponatremia. Eligibility criteria for optional tolvaptan treatment are outlined in [Appendix 5](#). Eligibility for optional tolvaptan treatment must be determined at the pre-treatment baseline visit (Day -4 to Day -1) of each dosing cycle. Eligible subjects can be treated at any time with optional tolvaptan during the 6-month core safety follow-up component. Optional tolvaptan treatment duration will be case-specific; it can be short-term or long-term, and consist of 1 or more treatment cycles. When a cycle with optional tolvaptan treatment is completed, including the Follow-up Phase visits, subjects will continue in the core safety component to complete the remainder of visits until Month 6. Within this trial, tolvaptan treatment will not extend beyond the 6-month core safety trial period. If the subject completes the 6-month core safety component while on optional tolvaptan treatment, the subject will complete the Month 6 core safety component visit, terminate treatment, and immediately enter the Follow-up Phase.

If a subject simultaneously participates in both core safety and optional tolvaptan treatment components, the visit days will be calculated between both components to ensure the assessments can be overlapped, where applicable.

3.1.2.1 Treatment Interruption on Day 30

Thirty days after the start of optional tolvaptan treatment, subjects will interrupt treatment for up to 2 doses (Days 31-32). The need for continuing treatment after this tolvaptan interruption will be assessed at minimum once daily (or more as needed) during this time.

Subjects who are expected to receive tolvaptan for greater than 30 days duration should demonstrate the need for continued treatment by discontinuing tolvaptan for up to 2 consecutive doses while undergoing close monitoring of serum sodium levels.

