1.	Has evidence of hypovolemia or intravascular volume depletion (eg, hypotension, clinical evidence of volume depletion, response to saline challenge); if the subject has systolic blood pressure or heart rate outside of the normal range for that age volume status should be specifically clinically assessed to rule out volume depletion.
2.	Has serum sodium < 120 mEq/L (mmol/L), with or without associated neurologic impairment (ie, symptoms such as apathy, confusion, or seizures)
3.	Use of potent CYP3A4 inhibitors in subjects ≤ 50 kg or moderate CYP3A4 inhibitors in subjects < 20 kg
4.	Lacks free access to water (inability to respond to thirst) or without ICU-level fluid monitoring and management
5.	Has a history or current diagnosis of nephrotic syndrome
6.	Has transient hyponatremia likely to resolve (eg, head trauma or post-operative state)
7.	Has hyperkalemia defined as serum potassium above the ULN for the appropriate pediatric age range

Ineligibility Criteria for Tolvaptan Treatment	
8.	Has eGFR < 30 mL/min/1.73 m ² calculated by the following equation: eGFR (mL/min/1.73 m ²) = 0.413 × height (cm)/serum creatinine (mg/dL)
9.	Has acute kidney injury defined as: 
 • Increase in serum creatinine by ≥ 0.3 mg/dL (≥ 26.5 μmol/L) within 48 hours; or • Increase in serum creatinine to ≥ 1.5 times baseline, which is known or presumed to have occurred within the prior 7 days; or • Urine volume < 0.5 mL/kg/h for 6 hours
10.	Has severe or acute neurological symptoms requiring other intervention (eg, hyperemesis, obtundation, seizures)
11.	Has had treatment for hyponatremia with: 
 • Hypertonic saline (including normal saline challenge) within 8 hours of qualifying serum sodium assessments; • Urea, lithium, demeclocycline, conivaptan, or tolvaptan within 4 days of qualifying serum sodium assessments; • Other treatment for the purpose of increasing serum sodium concurrent with dosing of trial medication
12.	Has anuria or urinary outflow obstruction, unless the subject is, or can be, catheterized during the trial
13.	Has a history of drug or medication abuse within 3 months prior to the pretreatment visit or current alcohol abuse
14.	Has a history of hypersensitivity and/or idiosyncratic reaction to benzazepine or benzazepine derivatives (such as benazepril)
15.	Has psychogenic polydipsia (subjects with other psychiatric illness may be included per medical monitor approval)

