16.	Has uncontrolled diabetes mellitus, defined as fasting glucose > 300 mg/dL (16.7 mEq/L [mmol/L])
17.	Has screening liver function values > 3 × ULN.
18.	Patient who has cirrhosis and meets any of the following conditions: a major GI bleed within the past 6 months, evidence of active bleeding (eg, epistaxis, petechiae/purpura, hematuria, or hematochezia), platelet count < 50,000/μL, or use of concomitant medications known to increase bleeding risk
19.	Has hyponatremia due to the result of any medication that can safely be withdrawn (eg, thiazide diuretics)
20.	Has hyponatremia (eg, hyponatremia in the setting of adrenal insufficiency, untreated hypothyroidism, or hypotonic fluid administration) that is most appropriately corrected by alternative therapies
21.	Is currently pregnant or breastfeeding
22.	Has any medical condition that, in the opinion of the investigator, could interfere with evaluation of the trial objectives or safety of the subjects
23.	Is deemed unsuitable for trial participation in the opinion of the investigator
24.	Participation in an investigational drug trial (other than a previous tolvaptan hyponatremia trial) within the past 30 days, without prior approval from the medical monitor
25.	Subjects < 4 years of age (or per local Health Authority age restrictions), weight < 10 kg, or who are unable to swallow tablets

AKI = acute kidney injury; eGFR = estimated glomerular filtration rate; GI = gastrointestinal;
ICU = intensive care unit; IRE = Immediately Reportable Event; ULN = upper limit of normal

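### Appendix 5, the criteria list reviewed before each tolvaptan cycle, does not match the mandatory demyelination-risk exclusions in Section 3.3.2

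*Protocol*

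**What the plan says.** Protocol Section 3.3.2 states the rule in mandatory terms: "those subjects who are at risk of developing cerebral demyelination will be ineligible for tolvaptan treatment". It then lists who this covers: severe hyponatremia at 120 mEq/L or lower, and "hypernatremia, hypoxemia, severe liver disease, alcoholism, severe burns, severe malnutrition, hypokalemia, diabetes, or renal failure".

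The operational criteria sit in Appendix 5. Section 3.3.1 sends the reader there "for optional tolvaptan treatment component eligibility requirements", Section 3.4.3 does the same for the exclusion criteria, and Section 3.7.2 does so for screening. Section 3.1.2 fixes the timing: "Eligibility for optional tolvaptan treatment must be determined at the pre-treatment baseline visit (Day -4 to Day -1) of each dosing cycle". Reviewing Appendix 5 is the first step of the pretreatment baseline visit in Section 3.7.3.2.1. A break of 72 hours or more starts a new cycle and triggers the review again.

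Three ineligibility criteria in Appendix 5 overlap with the Section 3.3.2 list but say something different:

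- Criterion 2: "Has serum sodium < 120 mEq/L (mmol/L), with or without associated neurologic impairment".
- Criterion 7: "Has hyperkalemia defined as serum potassium above the ULN for the appropriate pediatric age range".
- Criterion 16: "Has uncontrolled diabetes mellitus, defined as fasting glucose" above 300 mg/dL.

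Criterion 22 is a general clause: "Has any medical condition that, in the opinion of the investigator, could interfere with evaluation of the trial objectives or safety of the subjects". Criterion 23 is a second clause that rests on the investigator's opinion.

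**The concern.** Two current parts of the protocol give different answers on who may be dosed. The difference falls on the exclusions meant to prevent osmotic demyelination, which Section 5.3.1.1 itself describes as capable of causing serious brain injury or death. Staff confirm eligibility against Appendix 5. A bar that stands only in the population narrative of Section 3.3.2 can be missed by a site that works from the list it is told to review. Nothing in the protocol says which text governs when they differ.

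**Working it through.** There is no stated figure to reproduce. The check sets each item of the Section 3.3.2 list against Appendix 5.

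| Section 3.3.2 item | Appendix 5 | Result |
|---|---|---|
| Sodium 120 or lower | Criterion 2: below 120 | Different at exactly 120 |
| Hypokalemia | Criterion 7 covers high potassium only | No line |
| Hypoxemia | None | No line |
| Severe burns | None | No line |
| Severe malnutrition | None | No line |
| Diabetes, unqualified | Criterion 16: uncontrolled, fasting glucose above 300 mg/dL | Narrowed |
| Severe liver disease | Criteria 17 and 18: liver tests above 3 times ULN; cirrhosis with bleeding-risk features | Some counterpart |
| Alcoholism | Criterion 13: current alcohol abuse | Some counterpart |
| Renal failure | Criteria 8 and 9: eGFR below 30; acute kidney injury | Some counterpart |
| Hypernatremia | Excluded by the entry requirement of sodium below 130 | No practical gap |

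Tally: 4 with no line + 1 different cut-off + 1 narrowed + 3 with some counterpart + 1 with no practical gap = 10 items.

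**Sodium.** A child whose qualifying values are exactly 120 meets the entry criterion (below 130) and does not meet criterion 2 (below 120). Appendix 5 therefore admits the child. Section 3.3.2 (120 or lower) does not.

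**What Appendix 5 offers for the other five items.** For a child with hypokalemia, hypoxemia, severe burns, severe malnutrition or controlled diabetes, no criterion applies to the condition as such. Only criteria 22 and 23 remain. Both depend on the investigator's opinion and neither names these conditions.

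**Link back to Section 3.3.2.** Section 3.7.3.2 cites Section 3.3.2 at the qualification step, but for further assessments according to the cause of the hyponatremia. Hypokalemia, burns and malnutrition appear in Section 3.3.2 as demyelination risks, not as causes, so this reference does not clearly bring them into the review.

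**Laboratory tests.** Section 3.7.3.2.1 and Table 3.7.5.3-1 require ALT, AST, bilirubin, creatinine, serum sodium and, where applicable, a pregnancy test. Potassium is in neither place, although criterion 7 cannot be applied without it. As written, it would come from existing results seen in the chart review described in Section 3.7.5.8.

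**The case against.** The strongest reply is that Section 3.3.2 is itself operative. Investigators agree to follow the whole protocol, and a child barred by either text is barred. That stands. A reader might infer that the protocol leaves these children unprotected, and the documents do not support that reading. Initiation and titration also take place in hospital with frequent sodium checks (Section 3.7.3.2.2), which limits the harm from overly rapid correction. Those checks do not identify a child who should not have been started.

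A reader might also infer that cycles could be repeated with no potassium value at all. That goes too far. Criterion 7 needs a potassium result at each review, and Section 9.2 requires source notes to record review of all criteria before dosing. A value obtained for criterion 7 would also show a low potassium. What remains is that the laboratory tables omit the test and no criterion tells the site to act on a low result.

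Two figures might be taken as measures of risk. First, if sodium is reported in whole numbers (an assumption), Appendix 5 admits 120 to 129 (10 values) and Section 3.3.2 admits 121 to 129 (9 values). That counts reportable values, not children, and the protocol gives no sodium distribution. Second, Section 1.3 lists hypokalaemia among events above 5% on tolvaptan and not among those above 5% on placebo. It gives no rates, the events arose on treatment, and Section 1.3 also says that no pediatric trial had been completed. Neither figure shows how often a child would be affected.

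Finally, the Section 3.3.2 list reads partly like a general list of risk factors. It includes hypernatremia, which a qualifying child cannot have. Another paragraph of the same section makes exclusion for hypoxia only possible, as a risk factor for encephalopathy. Criterion 16 could be read as the working definition of diabetes. This is a fair argument for choosing one diabetes rule rather than assuming the wider one, but it does not explain the sodium cut-off or the four absent conditions.

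**Conclusion.** The point holds as an inconsistency between two current parts of the protocol on a safety exclusion. Six of the ten items in Section 3.3.2 are not carried faithfully into Appendix 5. The discretionary criteria do not cure this, because they replace a mandatory exclusion with a judgment. The practical risk rests on an assumption that the documents cannot test: that some sites would decide from Appendix 5 without returning to Section 3.3.2.

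The consequence for this trial is nil. SAP Section 5.1 records that the trial ended early with nobody treated in the optional component, so no child was exposed and no estimate is affected. The correction is still worth making, because it is cheap and the criteria text may be reused.

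**What to change.** Change Appendix 5 criterion 2 to a sodium of 120 mEq/L or lower. Add hypokalemia, for example potassium below the age-appropriate lower limit of normal, mirroring criterion 7. Add hypoxemia, severe burns and severe malnutrition. Choose one diabetes rule and state it identically in Section 3.3.2 and Appendix 5. List potassium among the required pretreatment laboratory tests for each cycle, accepting standard-of-care values, because criterion 7 already needs it.

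The cost is a text clarification and an occasional extra potassium result where none is in the chart. The added conditions and the sodium change remove nobody whom Section 3.3.2 does not already exclude. A routine glucose test for every child is not needed for this correction.
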